4.1.2.1 Secondary Endpoints

- Utilize FlowMet-R data to create a predictive model for the prognosis of vascular intervention within a three and six month timeframe from initial visit.
- Employ the predictive model of PAD severity to generate an ROC curve for diagnosis of significant stenosis (>50%) in the iliac, femoral, popliteal, peroneal, or tibial arteries.
- Conduct a correlation test between the predictive model of PAD severity and greatest percent stenosis in the iliac, femoral, popliteal, peroneal, or tibial arteries.

- Conduct a correlation test between changes in the predictive model of PAD severity and corresponding changes in ABI, TBI, and Rutherford Classification between any two study time points.

5. Study Design

This is a non-randomized, multi-center, longitudinal study of healthy subjects and subjects with PAD who are scheduled for ABI, TBI, and either Duplex ultrasound or Angiographic assessments in a vascular clinic. As detailed in the Event Schedules (Section 9.1), subjects will first be evaluated for study inclusion/exclusion. If the subject meets the inclusion criteria and wishes to enroll in the study, they will be asked to sign an informed consent form (ICF) and considered for enrollment. If the subject meets inclusion criteria and is enrolled, the subject will undergo approximately 3 minutes of FlowMet-R blood flow measurements in addition to their routine standard of care examination.

Subjects enrolled in the PAD cohort will be assessed according to Event Schedule A at approximately 0, 3 months, and 6 months. Subject follow ups must meet the scheduled time window within +/- 30 days. Subjects that require a vascular (re)intervention for PAD-related treatment before the final measurement (6 month follow up) will have pertinent data collected and saved in the study registry. The vascular procedure may change the timing with respect to the amount of months after baseline that the follow up visits occur. In that case, the standard of care follow up visits post intervention will be adhered to, and data will be collected from the follow up visits that correspond most closely to timepoints at 3 and/or 6 months post baseline visit.

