9.7.4 Duplex ultrasound

Color duplex ultrasound measurements shall be used to determine stenosis percentage and location, either during the visit itself or within 30 days prior of the patient visit. Duplex shall be acquired from all limbs enrolled in the study with PAD/CLI as defined via the definitions in Section 8.4. If duplex ultrasound is not available, X-ray angiography will be considered a suitable alternative for calculation of stenosis and location. Color duplex ultrasound imaging will be performed in a similar fashion as the study by Lewis, et al. [30]. First, the distal common femoral artery (CFA) will be imaged and the Doppler waveform (DW) assessed visually for any loss of triphasic flow due to significant iliac disease. If the DW shows indications of this, then the iliac arteries will be assessed for the presence of atherosclerotic disease. The scan will continue distally from the CFA assessing the superficial femoral artery (SFA), popliteal, anterior tibial, posterior tibial, and peroneal arteries in the longitudinal plane. The extent and severity of any arterial disease are assessed by measuring the peak systolic velocity (PSV) from the DW just proximal to and distal through the stenosis. For each measured artery, if perceptible stenosis exists, the location of maximum stenosis will be identified and PSV values distal and proximal to the arterial stenosis will be noted on the CRF. The shape of the waveform (i.e. monophasic, biphasic, or triphasic) measured distal to the stenosis shall also be noted. If no stenosis is noted, this will be indicated on the CRF.

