12.1.3 Analysis of Stenosis

For each artery measured using duplex ultrasound or arterial angiography, the ratio of the PSV distal to the most prominent stenosis to the PCV proximal to the stenosis will be computed (if applicable). The percent stenosis in such arteries will be computed two ways: (1) Percent stenosis = $PSV_{distal}/PSV_{proximal}$, or (2) using the diameter reduction value from Table 3, reprinted from [35].

	Diameter reduction	Waveform	Special broadcasting	PSV distal/PSV proximal
Normal	0	Triphasic	Absent	+++ No change
Mild	1%–19%	Triphasic	Present	<2:1
Moderate	20%–49%	Biphasic	Present	<2:1
Severe	50%–99%	Monophasic	Present	>2:1*

PSV, Peak systolic velocity.

* > 4:1 suggests >75% stenosis, >7:1 suggests > 90% stenosis.

Table 3: Criteria for determining arterial stenosis using peak systolic velocity (PSV) measurements.

Classification of the percent stenosis or presence of greater than 50% stenosis for each limb (used to generate corresponding ROC curve or correlation coefficient) may be determined by either considering a single artery of interest or by considering the artery in each limb with the greatest percent stenosis.

13. Ethics

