4.1.2.1 Secondary Endpoints

- Utilize FlowMet-R data to create a predictive model for the prognosis of vascular intervention within a three and six month timeframe from initial visit.
- Employ the predictive model of PAD severity to generate an ROC curve for diagnosis of significant stenosis (>50%) in the iliac, femoral, popliteal, peroneal, or tibial arteries.
- Conduct a correlation test between the predictive model of PAD severity and greatest percent stenosis in the iliac, femoral, popliteal, peroneal, or tibial arteries.
- Conduct a correlation test between changes in the predictive model of PAD severity and corresponding changes in ABI, TBI, and Rutherford Classification between any two study time points.

5. Investigation Plan

This study is a non-randomized, multi-center, longitudinal study of healthy subjects and subjects with PAD who are scheduled for ABI, TBI, and either Duplex ultrasound or Angiographic assessments in a vascular clinic. Subjects will first be evaluated for study inclusion/exclusion. If the subject meets the inclusion criteria and wishes to enroll in the study, they will be asked to sign an informed consent form (ICF) and considered for enrollment. If the subject meets inclusion criteria and is enrolled, the subject will undergo approximately 3 minutes of FlowMet-R blood flow measurements in addition to their routine standard of care examination.

Subjects enrolled in the PAD cohort will be assessed according to Event Schedule A in the clinical investigation protocol (CIP) at approximately 0, 3 months, and 6 months. Subject follow ups must meet the scheduled time window within +/- 30 days. Subjects that require a vascular (re)intervention for PAD-related treatment before the final measurement (6 month follow up) will have pertinent data collected and saved in the study registry. The vascular procedure may change the timing with respect to the amount of months after baseline that the follow up visits occur. In that case, the standard of care follow up visits post intervention will be adhered to, and data will be collected from the follow up visits that correspond most closely to timepoints at 3 and/or 6 months post baseline visit.

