7.10.2 Secondary Objectives

The secondary endpoints will be analyzed as follows:

1. The capability of the acceleration time from the FlowMet-R device to predict a vascular intervention or amputation will occur within three and six months following initial visit will be determined using the AUC from an ROC curve where the endpoint is vascular intervention or amputation within 7 months, which is the end of the 6 month follow-up window. The 95% CI of the AUC will be derived using the method described in DeLong, et al (1998) [15].
2. The capability of the acceleration time from the FlowMet-R device to predict a $\geq 50\%$ stenosis determined using the AUC from an ROC curve where the endpoint is vascular intervention or amputation within 7 months, which is the end of the 6 month follow-up window. The 95% CI of the AUC will be derived using the method described in DeLong, et al (1998) [15].
3. The correlations between the acceleration time from the FlowMet-R device and peripheral artery stenosis, changes in ABI, and changes in TBI will be computed using Pearson correlations. The changes for ABI and TBI will be as follows: 0 to 3 months, 0 to 6 months, and 3 to 6 months.
4. The correlation between the acceleration time from the FlowMet-R device and changes in Rutherford Classification will be computed using the Spearman correlation. The changes for Rutherford Classification will be as follows: 0 to 3 months, 0 to 6 months, and 3 to 6 months.

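### Protocol 12.1.3 lets the limb's stenosis label come from one unnamed artery, which conflicts with the secondary endpoints, and no SAP section withdraws the option

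*Protocol*

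**What the plan says.** Protocol 12.1.3 sets how percent stenosis, or the presence of more than 50% stenosis, is assigned "for each limb (used to generate corresponding ROC curve or correlation coefficient"). It says that this "may be determined by either considering a single artery of interest or by considering the artery in each limb with the greatest percent stenosis". It does not say which artery is of interest, who chooses it, or which option applies to which analysis.

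The endpoints are narrower. Protocol 4.1.2.1 plans to "generate an ROC curve for diagnosis of significant stenosis (>50%) in the iliac, femoral, popliteal, peroneal, or tibial arteries". The correlation endpoint, worded the same way in SAP 4.1.2.1, uses the "greatest percent stenosis in the iliac, femoral, popliteal, peroneal, or tibial arteries".

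The analysis text in SAP 7.10.2 does not carry a label rule. Item 3 refers only to "The correlations between the acceleration time from the FlowMet-R device and peripheral artery stenosis" and does not say how a limb with several imaged arteries is reduced to one value. Item 2, on predicting stenosis, reads "stenosis determined using the AUC from an ROC curve where the endpoint is vascular intervention or amputation within 7 months", which is not a stenosis endpoint. The cut-off also differs: above 50% in section 4.1.2.1 of both documents and in Protocol 12.1.3, but 50% or above in SAP 7.10.2 item 2. The severe class in the Protocol 12.1.3 table starts at 50%.

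**The concern.** A limb-level ROC curve needs one reference label per limb. Here the endpoint defines that label over the whole arterial tree of the leg, while the section describing its derivation permits a different one. The two labels disagree whenever the chosen artery is not the worst artery.

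FlowMet-R is read at the toe, downstream of every artery on the list. If the reading responds to disease anywhere upstream, a limb with a severe femoral lesion will tend to give an abnormal reading. Under the single-artery option that limb counts as negative if another artery was chosen and is below the cut-off. The device is then charged with a false positive that the endpoint would count as a correct detection. For the correlation, the limb receives the chosen artery's value, which can only equal or fall below the greatest stenosis.

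**Working it through.** The documents give no sample size, expected AUC or per-artery prevalence for the stenosis endpoint, so there is no plan figure to reproduce. The check is a comparison of texts, followed by an illustration.

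**1. Texts side by side**

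| Place | ROC label | Correlation variable |
|---|---|---|
| Protocol and SAP 4.1.2.1 | More than 50% in the listed arteries, joined by 'or' | Greatest percent stenosis over the listed arteries |
| Protocol 12.1.3 | One artery, or the worst artery | One artery, or the worst artery |
| SAP 7.10.2 | Item 2: intervention or amputation named as endpoint | Item 3: no artery rule |

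The conflict is explicit for the correlation. For the ROC it follows from reading the list as any listed artery. SAP 7.7 and 7.8 derive ABI, TBI and acceleration time, but no SAP section derives stenosis. SAP 7.12, the list of changes to the planned analysis, does not mention the option.

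**2. The data allow the endpoint's label.** Protocol 9.7.4 continues from the common femoral artery, "assessing the superficial femoral artery (SFA), popliteal, anterior tibial, posterior tibial, and peroneal arteries", and adds the iliac arteries when the femoral waveform suggests disease. The worst imaged artery can therefore be derived.

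**3. Illustration of size**

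Inputs from the documents:
- 240 PAD limbs and 160 control limbs (Protocol 12.1.1).
- Healthy subjects with normal ABI and TBI are assumed to have no significant stenosis (section 5 of both documents), and the full analysis set serves all analyses (SAP 7.1.3). Control limbs therefore enter as negatives.

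Assumptions:
- Six arteries: iliac, superficial femoral, popliteal, anterior tibial, posterior tibial and peroneal.
- Each artery of a PAD limb has an independent probability q of more than 50% stenosis, with q from 0.10 to 0.25.
- The AUC against the any-artery label is 0.75, and the score relates equally to stenosis in any artery.

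Formulas:
- PAD limbs negative on the chosen artery: 240(1 − q).
- Share of those with more than 50% stenosis in one of the other five: 1 − (1 − q)^5.
- Contamination c: diseased labelled negatives divided by all labelled negatives, controls included.
- AUC read: (1 − c) × 0.75 + c × 0.5 = 0.75 − 0.25c. Every limb positive on one artery is also positive on the any-artery label, so the error affects only the negatives.

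| q | PAD limbs labelled negative | Share diseased elsewhere | Diseased labelled negatives | All labelled negatives | c | AUC read |
|---|---|---|---|---|---|---|
| 0.10 | 216 | 0.41 | 88 | 376 | 0.24 | 0.69 |
| 0.25 | 180 | 0.76 | 137 | 340 | 0.40 | 0.65 |

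**4. Effect of correlation between arteries.** A separate simulation used five arteries, 20% prevalence in each, an exchangeable normal threshold model and the same limb numbers. The labelled negatives number 160 + 240 − 48 = 352. The diseased limbs among them are 113, 86 and 60 at correlations of 0, 0.3 and 0.6, so c is 0.32, 0.24 and 0.17. A starting AUC of 0.80 would read 0.70, 0.73 and 0.75. Correlation shrinks the loss but does not remove it.

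**The case against.** The strongest reply is that the endpoint governs. SAP 4.1.2.1 repeats the greatest-stenosis definition, the SAP never repeats the single-artery option, and Protocol 12.1.3 says only that the label may be formed that way, with the second option agreeing with the endpoint. Much of this stands. A reader might infer that the SAP leaves the correlation variable undefined, or that the plan will mislabel limbs. The documents support neither: the SAP defines the variable in its endpoint list, and the conflicting label is permitted, not required. What remains is that Protocol 12.1.3 is the only text describing how the label is formed, and nothing withdraws its first option.

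A reader might also infer that the artery could be picked after the results are seen, to obtain the best AUC. No text says so. The highest-AUC rule in Protocol 12.1.2 concerns the classification algorithm for PAD and CLI. That inference also sits badly with the attenuation argument: if every single-artery label lowers the AUC, choosing the highest would, sampling noise aside, lead back to the worst-artery label.

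A third tempting step is to count imaged PAD limbs only, which gives 41–76% diseased negatives and an AUC of 0.65–0.56. That leaves out the control limbs, which the documents treat as free of significant stenosis.

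Finally, these are secondary objectives with no success criterion, and SAP 7.2 presents the objectives descriptively. That limits the consequence.

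**Conclusion.** The point holds as an unresolved conflict. Protocol 12.1.3 permits a limb label that contradicts the endpoints in section 4.1.2.1 of both documents, and neither SAP 7.10.2 nor SAP 7.12 closes it. If the option were used, affected limbs would be labelled as not having more than 50% stenosis. It would be too strong to call them stenosis-free, because the chosen artery may still carry a lesser stenosis.

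Under the stated assumptions, about 24–40% of labelled negatives would be diseased and an AUC of 0.75 would read about 0.69–0.65, a loss of 0.06–0.10. Prevalence, independence, the count of six arteries and the starting AUC are assumptions, not document figures. Correlation between arteries reduces the loss. Its direction rests on the toe reading reflecting disease in any upstream artery. The primary PAD and CLI analyses are not affected.

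**What to change.** - Protocol 12.1.3: delete the single-artery option for the ROC and correlation endpoints.
- SAP 7.10.2 items 2 and 3: state that the limb label is the greatest percent stenosis over all imaged iliac, femoral, popliteal, peroneal and tibial arteries.
- SAP 7.10.2 item 2: in the same edit, replace the intervention or amputation endpoint with this stenosis label. Otherwise the item would hold two incompatible endpoints.
- Cut-off: use one throughout. Keeping the value above 50% that stands in section 4.1.2.1 of both documents and in Protocol 12.1.3 means changing only SAP 7.10.2 item 2. Choosing 50% or above means changing the other three places.
- Report any single-artery result as descriptive only, with the artery named in advance.

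The cost is a few sentences across the two documents, with the protocol change submitted to the IRBs under Protocol 14.6. No new data are needed, since stenosis is already recorded by artery.

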13.1 Statement(s) of Compliance

This study will be conducted in compliance with Good Clinical Practice. GCP includes review and approval by an independent IRB before initiating a study, continuing review of an ongoing study by and IRB, and obtaining and documenting the freely given informed consent of a subject before initiating the study.

The FlowMet-R study is compliant with ISO 14155. This includes the protection of the rights, safety and well-being of human subjects, controls to ensure the scientific conduct and credibility of the clinical investigation and the definition of responsibilities of the sponsor and investigator. In accordance with ISO 14155, the sponsor shall avoid improper influence on, or inducement of, the subject, monitor, any investigator or other parties participating in or contributing to the clinical investigation.

The principles of the Declaration of Helsinki have been implemented throughout the informed consent process, IRB approval, and study training.

In addition to the regulatory requirements outlined above, the study will be conducted according to federal, national and local laws, regulations, standards, and requirements of the United States, where the study is being conducted. These include, but are not limited to:

- 21 CFR Part 11: Electronic Records, Electronic Signatures
- 21 CFR Part 50: Protection of Human Subjects
- 21 CFR Part 54: Financial Disclosure by Clinical Investigators
- 21 CFR Part 56: IRB
- Principles of the Declaration of Helsinki

14. Study Administration

14.1 Monitoring

The FlowMet-R study will be monitored by the sponsor and a third-party research organization, [REDACTED], and made available for monitoring, auditing, IRB review and regulator inspection by providing direct access to study related source data. Site monitors will visit the site periodically to ensure adherence to the protocol.

14.2 Data Management

An EDC system will be created that contains the case report forms (CRF) to be filled out for each enrolled subject. The sites may optionally use a paper-based form for collecting key data from the patient during the visit, then upload the results to the EDC post-visit.

All records and other information about subjects participating in this study will be treated as confidential. Procedures in the CIP require source documentation. Source documentation will be maintained at the study site. Source documents, which may include worksheets and subject medical records, must be created and maintained by the investigational study site team.

The investigator will clearly mark clinical records to indicate that the subject is enrolled in this clinical investigation. The data reported on the CRFs shall be derived from source documents and be consistent with these source documents, and any discrepancies shall be explained in writing.

14.3 Direct Access to Source Data/Documents

When applicable, the monitors, auditors, the IRB, the Office of Human Subjects Protection (OHRP) of the Department of Health and Human Services as well as the Food and Drug Administration (FDA) will be granted direct access to medical records for verification of the research procedures and data.

14.4 Confidentiality

The study will be conducted in a manner consistent with the federal Health Insurance Portability and Accountability Act (HIPAA). Only non-identifiable health information will be collected and stored in the EDC database. The research staff at individual sites may use and share information to ensure research meets legal, institutional, or accreditation requirements. If the research team uncovers abuse, neglect, or reportable diseases, this information may be disclosed to appropriate authorities. As part of the study, the PI, study team, and others may disclose non-identifiable protected health information to the following:

- The commercial sponsor and/or their representative Medtronic Inc.
- Contract Research Organization (whose job is to help organizations fulfill their responsibilities in the research and development process); [REDACTED]
- The United States Food and Drug Administration
- The United States Department of Health and Human Services and the Office of Human Research Protection (OHRP).

In all disclosures outside of individual study sites, no subject shall be identified by name, social security number, address, telephone number, or any other direct personal identifier unless disclosure of the direct identifier is required by law. OHRP and FDA are authorized to remove information with identifiers if necessary to complete their task.

14.5 Liability

14.6 Liability provisions are expressed in each site clinical trial agreement. CIP Amendments

- Any revisions or amendments to the CIP or IC document, along with a statement of justification for the changes, will be submitted to all affected IRBs. All amendments to the CIP shall be agreed upon between Medtronic and the principal investigator(s), or the coordinating investigator. Approval by IRB must be obtained prior to implementing a CIP revision at the study site.

14.7 Record Retention

The investigator will maintain complete and accurate study records in an encrypted file located exclusively at the clinic for 2 years following study closure. The investigator should take measures to prevent accidental or premature destruction of documents. Should the investigator wish to assign the study records to another party or move them to another location, advance written notice must be given to Medtronic.

Medtronic will retain the study records according to Medtronic corporate policy and record retention schedule.

14.8 Suspension or Early Termination

14.8.1 Planned Study Closure

Study Closure is a process initiated by distribution of a study closure letter. Study closure is defined as closure of a study that occurs when Medtronic requirements have been satisfied per the CIP. Ongoing IRB oversight is required until the overall study closure process is complete.

3.1	MAJOR CHANGES			
	Migration to Medtronic Template	Acquisition of LAS by MDT complete	Informed Consent Form	
	Changed FlowMet assessment procedure to implement the standard of care rest period for ABI/TBI instead of FlowMet-specific 5 minute rest period. The same rest period may be applied for FlowMet and ABI/TBI measurements.	Changed to ensure sites can follow their own specific standard of care for ABI/TBI.		
	Created a health-cohort specific procedures flowchart.	Improved readability		
	Added exclusion of PAD cohort: 
 – Subject may not have revascularization surgery within the last 90 day – Subject cannot lay safely in supine position 	Added language to avoid ambiguity in patient symptoms and to avoid putting patient in supine position who may not be able to safely be supine for required length of time.		
	Added exclusion of Healthy cohort 
 – Subject does not have suitable finger or toes to attach the probe – Subject is under 40 years old 	Added for clarity and to ensure healthy cohort maintains an age-matched population with PAD cohort.		

FlowMet-R Blood Flow Measurement for PAD and CLI Clinical Investigation Plan

Version 3.1

Page 41 of 42

Form

Medtronic

	Changed FlowMet assessment procedure to note that if 5 or more repeated attempts are made with poor-quality data, then the clinician will choose the optimal record to the best of their knowledge.	Added to ensure procedure was in place for the rare occurrence where FlowMet readings cannot accurately be obtained after 5 attempts.		
	Changed date requirements of ultrasound or angiographic imaging from within 24 hours to 30 days.	Loosened this restriction to improve patient enrollment. This restriction was determined able to be reduced because very little change is expected to occur in the stenosis % in chronic PAD patients over the prior 30 days before their imaging exam. Additionally, 30 days is a commonly accepted timeframe for validity of stenosis imaging tests used in similar PAD studies.		
MINOR CHANGES				
	Created separate event schedule C specifically for healthy cohort.	Additional language added for readability.		
	Specified patients enrolled in PAD cohort cannot be grouped into healthy cohort, even after their PAD is treated.	Always intended this way but provided additional language for clarity.		
	Request digitized copy of intraprocedural log for patient registry.	Electronic copy is required for storage in edc system.		

FlowMet-R Blood Flow Measurement for PAD and CLI Clinical Investigation Plan

Version 3.1

Page 42 of 42

Form

Medtronic

	Clarification that follow-up visits will be conducted as per standard of care post-procedure, and that the visits that most closely correspond to the 3- and 6- month timepoints after initial visit will be used.	Made follow up visit window less strict to better accommodate Covid situation and reduce dropout rate.		
	Inclusion Criteria: Specified that PAD cohort must meet PAD positive criteria described in protocol.	In practice this has always been the case, added explicit language for clarity		
	Added procedure if FlowMet-R system needs servicing or replacement.	Added language to improve procedure and timeline in case FlowMet system requires servicing.		
	Specified wound-specific information (wound grade, infection grade, healing status) that is required as part of medical history.	Provided additional details on medical history questions for clarity.		
	Added more specific information requests about adverse event handling (whether device related or serious).	Clarification on how to treat adverse events.		
	Added language for protocol deviation information.	Improved details for submitting protocol deviation.
